10.6.3.5. Delayed Graft Function Endpoints

DGF Endpoints
DGF Following Deceased Donor Kidney Transplantation

 DGF following deceased donor kidney transplantation will be identified using the following combination of responses to questions on the Kidney Transplant eCRF form: 
 Donor source of transplant = either ['Deceased donor – donation after cardiac death (DCD)' or 'Deceased donor – donation after brain death (DBD)']

DGF Endpoints

and
 
 ○ Did the subject have delayed graft function requiring dialysis within the first 7 days = 'Yes'
Duration of DGF

 • The duration of DGF following deceased donor kidney transplantation will be defined as date of last dialysis after transplant (from the Kidney Transplant eCRF form) – kidney transplant date + 1 day

10.6.3.6. Dose Adjustment Scheme Endpoints

Dose Adjustment Scheme Endpoints																				
General																				

 • The IRT system assigns all randomized treatment doses in accordance with the dose adjustment scheme specified in the protocol. • During the study, it is possible for subjects to change randomized treatment doses at both scheduled and unscheduled visits. • Sites are instructed to complete an exposure record every time dosing instruction is received from the IRT, with the exception of re-dispensing situations where the subject is instructed to continue using the same randomized treatment. 																				
Daprodustat Doses																				

Sites will enter the dose of daprodustat into exposure records – the daily frequency will be auto-populated for this randomized treatment. The dose steps of daprodustat are shown below:
 
  
 Total Daily Dose	How Administered	
   
 1 mg	single 1 mg tablet	
 
 2 mg	single 2 mg tablet	
 
 4 mg	single 4 mg tablet	
 
 6 mg	single 6 mg tablet	
 
 8 mg	single 8 mg tablet	
 
 10 mg	single 10 mg tablet	
 
 12 mg	two 6 mg tablets	
 
 16 mg	two 8 mg tablets	
 
 24 mg	three 8 mg tablets	
  
	Total Daily Dose	How Administered	1 mg	single 1 mg tablet	2 mg	single 2 mg tablet	4 mg	single 4 mg tablet	6 mg	single 6 mg tablet	8 mg	single 8 mg tablet	10 mg	single 10 mg tablet	12 mg	two 6 mg tablets	16 mg	two 8 mg tablets	24 mg	three 8 mg tablets
Total Daily Dose	How Administered																			
1 mg	single 1 mg tablet																			
2 mg	single 2 mg tablet																			
4 mg	single 4 mg tablet																			
6 mg	single 6 mg tablet																			
8 mg	single 8 mg tablet																			
10 mg	single 10 mg tablet																			
12 mg	two 6 mg tablets																			
16 mg	two 8 mg tablets																			
24 mg	three 8 mg tablets																			
Darbepoetin Alfa Doses																				

Sites will enter the dose and frequency of each dose of darbepoetin alfa into exposure records. The dose steps of darbepoetin alfa (including the corresponding total 4-weekly doses) are shown below:
 
  
 Total 4-Weekly Dose	Pre-filled Syringe Dose and Frequency	
   
 20 µg	20 µg every 4 weeks	
 
 30 µg	30 µg every 4 weeks	
 
 40 µg	40 µg every 4 weeks	
 
 60 µg	60 µg every 4 weeks	
 
 80 µg	80 µg every 4 weeks	
  
	Total 4-Weekly Dose	Pre-filled Syringe Dose and Frequency	20 µg	20 µg every 4 weeks	30 µg	30 µg every 4 weeks	40 µg	40 µg every 4 weeks	60 µg	60 µg every 4 weeks	80 µg	80 µg every 4 weeks								
Total 4-Weekly Dose	Pre-filled Syringe Dose and Frequency																			
20 µg	20 µg every 4 weeks																			
30 µg	30 µg every 4 weeks																			
40 µg	40 µg every 4 weeks																			
60 µg	60 µg every 4 weeks																			
80 µg	80 µg every 4 weeks																			

Dose Adjustment Scheme Endpoints	
100 µg	100 µg every 4 weeks
150 µg	150 µg every 4 weeks
200 µg	100 µg every 2 weeks
300 µg	150 µg every 2 weeks
400 µg	100 µg every 1 week
Assigned Dose At A Scheduled Visit	

 The assigned dose at a particular visit refers to the dose the subject received at that visit, as recorded in the eCRF. The assigned dose at Visit X is the dose from the earliest exposure record with a start date on or after the Visit X date, but before the Visit X+1 date. 
 For example, the assigned dose at the Week 28 visit is the dose from the earliest exposure record with a start date on or after the Week 28 visit date, but before the Week 32 visit date. 	
Most Recent Dose Prior to A Scheduled Visit / End of Treatment	

 The most recent dose prior to a particular visit refers to the dose the subject received in the period directly preceding the visit, as recorded in the eCRF. The most recent dose prior to Visit X is the dose from the latest exposure record with a start date that is on or after the Visit X-1 date and before the Visit X date. 
 For example, the most recent dose prior to Week 28 is the dose from the latest exposure record with a start date that is on or after the Week 24 visit date and before the Week 28 visit date. If a subject permanently stops randomized treatment after Visit X-1 and on or before Visit X, the most recent dose prior to Visit X will be the dose from the subject's final exposure record. 	
Two Approaches to Dose Adjustment Summaries	

 The first approach counts all dose adjustments, including dose adjustments related to periods of dose holds (i.e., IRT assignment of a 0-dose). The second approach does not count dose adjustments related to periods of dose holds. However, should the dose that a subject receives following a period of dose hold be different from the dose the subject received before the dose hold, this would still count as a dose adjustment in this approach. 	
Number of Dose Adjustments per Year During Day 1 - < End of Treatment	

 The number of dose adjustments per year will be determined by dividing the total number of dose adjustments between Day 1 and End of Treatment by [(Treatment Stop Date – Day 1 date + 1 day) / 365.25]. 	
Dosing Algorithm Update	

 The dosing algorithm update went into effect on different dates at different sites, due to variable approval times. The IRT records the date that each site changed algorithms. Subjects' randomization dates and Hgb assessment dates will be compared to their site's date of algorithm change. Any randomization/Hgb assessment dates before the day of the site's algorithm change are considered to have occurred under the original algorithm. Any randomization/Hgb assessment dates on or after the day of the IRT algorithm change are considered to have occurred under the updated algorithm. The 95% prediction interval for Hgb values at a visit provides an estimate of the range where future Hgb values would occur, with a probability of 95%. The 95% prediction interval for future Hgb values can be calculated using the approach described in (Francq, 2019), where the 	

Dose Adjustment Scheme Endpoints
prediction interval at Visit x is calculated using adjusted mean Hgb value at Visit $x \pm 1.96 * \text{sqrt}(\text{standard error}^2 + \text{total variance at Visit } x)$. Due to the use of an unstructured covariance matrix (Section 8.1.2), the total variance at Visit x is found at (x, x) on the diagonal of the R matrix.

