The number and percentage of subjects with a Hgb value ≥ 12 g/dL during the study will be summarized by clopidogrel co-administration, and by treatment group using evaluable Hgb values (see Section 10.6.3). Clopidogrel co-administration is defined as subjects who

use clopidogrel once or more either at randomization or during the on-treatment state for concomitant medications (see Section 10.4.1).

The number and percentage of subjects who had dose adjustments (decreases, increases, no change) will be summarized at Week 2 and Week 4 by baseline clopidogrel co-administration, and by treatment group. The number of dose decreases per subject will be summarized for baseline clopidogrel users, using mean, standard deviation, minimum, P25, median, P75, and maximum by baseline clopidogrel use, and by treatment group, for Day 1 to Week 12. Baseline clopidogrel co-administration is defined as subjects who use clopidogrel at randomization.

The number and percentage of subjects had dose adjustments (decreases, increases, no change) will be summarized for new clopidogrel users, who started clopidogrel after randomization, during the on-treatment state for concomitant medications (see Section 10.4.1), by treatment group. If they started clopidogrel within two weeks of a scheduled visit (i.e. visit date - 2w < clopidogrel start date \leq visit date + 2w), they will be summarized in the following scheduled visit. The number of dose decreases per subject will also be summarized for these new clopidogrel users using mean, standard deviation, minimum, P25, median, P75, and maximum by clopidogrel use, and by treatment group, for clopidogrel use start date to clopidogrel use + Week 12.

The median assigned dose by treatment, by clopidogrel co-administration, and visit will be displayed graphically for each scheduled study visit from day 1 to week 52 using a line plot. The line plot of median assigned dose along with the first and the third quartiles by time will include vertical reference lines to identify the EP as well as the number of subjects by treatment group contributing to each median value. This plot will be overlaid on a graph of corresponding mean Hgb values by visit. Clopidogrel co-administration here is defined as subjects who use clopidogrel once or more, at randomization, or during the on-treatment state for concomitant medications (see Section 10.4.1) in the first year of the study.

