4. Repeat pregnancy test prior to placebo run in or randomized treatment re-administration if it is disrupted for >7 days and there was also a lapse in contraceptive use, regardless of the reason for the disruption. If a subject becomes post menopausal (as defined in Protocol Appendix 6) during the study pregnancy tests are no longer required.
5. See details on hematology and clinical chemistry in Protocol Section 7.4.11.
6. HbA1c assessment only in subjects with diabetes on Day 1 or diagnosed during the study.
7. Subjects transitioning to dialysis must follow the time and events schedule detailed in Protocol Appendix 7. See also Protocol Section 6.13 for additional details.
8. Only SAEs assessed as related to study participation or a GSK product are collected at this visit. See Protocol Section 7.4.3.1 for additional details.
9. If dose does not change, then randomized treatment is returned to subject.
10. If a subject lost their placebo run in or randomized treatment, it is not necessary to perform the unscheduled visit assessments other than dispensing randomized treatment.
11. Required only if dose is changed or randomized treatment is dispensed. Compliance checking will be required when a dose of randomized treatment is changed.
12. Additional visits to check Hgb and dispense randomized treatment (where directed by the IRT system) are required under the circumstances described in Protocol Appendix 5. Hematology and chemistry samples are not required.
13. All assessments pre-dose.
14. Further visits every 12 weeks as required.
15. Investigator will inform subject when to attend this End of Study visit (Protocol Section 6.3.4).
16. Ultrasound of the kidneys and adrenal glands will be performed as early as 6 weeks prior to the Day 1 visit. If results of kidney and adrenal ultrasound require follow-up testing, then the run-in period can be extended by 1 additional week. A documented ultrasound of the kidneys within the 6 months prior to screening may be used to assess entry criteria, provided the size and cyst category has been reported. If a more sensitive imaging study [e.g., magnetic resonance imaging (MRI), computed tomography.(CT)] has been performed within this timeframe and a report is available, this may be used in place of the ultrasound.. See Protocol Section 7.4.10.
17. Day 1 ECG may be performed as early as the Week – 4 visit through the Day 1 visit; If performed on Day 1, it must be over-read prior to randomization.

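### The assigned-dose rule has no carry-forward, so subjects whose dose is unchanged at Week 2 probably get no Week 2 dose, or the dose of a later unscheduled change

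*SAP*

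**What the plan says.** Section 10.6.3.6 first gives the meaning of the variable: "The assigned dose at a particular visit refers to the dose the subject received at that visit, as recorded in the eCRF". It then gives the derivation, the "dose from the earliest exposure record with a start date on or after the Visit X date, but before the Visit X+1 date", with Week 28 to Week 32 as the worked example. Nothing is said for a subject with no record in that window.

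The same section tells sites to complete an exposure record at each dosing instruction from the IRT, "with the exception of re-dispensing situations where the subject is instructed to continue using the same randomized treatment". It also notes that "it is possible for subjects to change randomized treatment doses at both scheduled and unscheduled visits".

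In the schedule of assessments (Section 10.2.1.1), the dispensing cell carries footnote 9 at Week 2 and at unscheduled visits, and at no other scheduled visit: "If dose does not change, then randomized treatment is returned to subject". The compliance cell at Week 2 carries footnote 11: "Required only if dose is changed or randomized treatment is dispensed".

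The most recent dose before a visit comes from the "latest exposure record with a start date that is on or after the Visit X-1 date and before the Visit X date". Its only fallback is for subjects who stop randomized treatment permanently in that interval.

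Section 8.1.2.2 plans assigned-dose tables, stacked bars and median plots over all scheduled visits from Day 1, and a median plot of most recent dose overlaid on Hgb.

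**The concern.** The definition and the derivation ask for different things. The first wants the dose the subject is on as a result of the visit; the second finds it only if a new record was opened. Where continuing on the same dose opens no record, being in the summary depends on having had a dose change, which is the very thing these displays are meant to describe.

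At Week 2 the dose distribution would then represent subjects whose dose changed, not the arm. The contributing number would fall sharply at that one visit, and the median could appear to jump and then return. If the share of changes differed between daprodustat and darbepoetin alfa, the side-by-side display would be distorted as well. The median-dose plots from Day 1 to Week 52 in the phosphate binder analyses (Section 8.1.3) and the clopidogrel analyses (Section 8.2.9) also use assigned dose and would show the same artefact at Week 2.

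**Working it through.** The SAP states no figure on this point, so there is none to reproduce. The check applies the rules literally.

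**Step 1: where can a record be absent?** The IRT is contacted at Week 2, so a record is due unless the re-dispensing exception applies. That exception concerns being told to continue the same treatment; footnote 9 describes unchanged supply going back to the subject; footnote 11 waives the compliance check unless the dose changes or supply is dispensed. The three fit together: an unchanged dose at Week 2 opens no record. At the other scheduled visits supply is dispensed without footnote 9, so a record is expected.

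**Step 2: three example subjects.** Week 2 is day 15 and Week 4 is day 29. Dose levels 2 and 1 are arbitrary labels.

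| Subject | Records (start day: level) | Week 2 dose in force | Week 2 assigned dose under the SAP rule |
|---|---|---|---|
| A, unchanged at Week 2 | 1: 2; 29: 2 | 2 | missing |
| B, changed at Week 2 | 1: 2; 15: 1; 29: 1 | 1 | 1 |
| C, unchanged at Week 2, unscheduled change on day 22 | 1: 2; 22: 1; 29: 1 | 2 | 1 (wrong) |

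Only B is right. All three get the correct Day 1 and Week 4 assigned dose.

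**Step 3: most recent dose before Week 4.** The rule needs a record starting from day 15 to day 28. A has none and is missing. B gives 1. C gives 1, which is correct, because level 1 is what C was on just before Week 4. So this rule can lose subjects but does not report a wrong dose.

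**Step 4: size, by assumption only.** Let u be the share unchanged at Week 2 and s the share of those with an unscheduled change before Week 4. Neither is in the SAP. Per 1,000 subjects:

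- number summarized at Week 2: N = 1000(1 − u) + 1000·u·s
- share of N whose value is not the Week 2 dose: 1000·u·s / N

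| u | s = 0: N | s = 5%: N | s = 5%: share not the Week 2 dose |
|---|---|---|---|
| 50% | 500 | 500 + 25 = 525 | 25/525 = 4.8% |
| 70% | 300 | 300 + 35 = 335 | 35/335 = 10.4% |
| 90% | 100 | 100 + 45 = 145 | 45/145 = 31.0% |

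**Step 5: after the repair.** If the dose of the ongoing record is carried forward and the day 22 record is not attributed to Week 2, A and C both get level 2 and B keeps level 1. All three are then correct.

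**The case against.** The strongest reply is that the key link is not stated. Footnote 9 speaks of supply being returned, footnote 11 treats dispensing as a separate event, and re-dispensing might mean replacing lost supply (footnote 10, or the kit replacements in Section 6.2.6). If so, every Week 2 IRT contact would open a record and the gap would vanish. The eCRF completion instructions, which would settle it, are not in the SAP. This stands as a limit on certainty. It does not remove the point: the exception is worded around continuing the same treatment, which is what happens at a Week 2 hand-back, and the derivation has no provision for a missing record either way.

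A second reply is that Section 6.2.6 merges IRT and eCRF data. That text serves the exposure, compliance and discrepancy displays and does not amend Section 10.6.3.6, which specifies the dose recorded in the eCRF.

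A third is that the reach is small. This stands. Section 2.2 lists these as exploratory endpoints without planned testing, and the median plots print the contributing number, so a drop at Week 2 would be visible.

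The forward window also does something useful: it catches a new dose whose record starts a day or more after the visit. Taking only records that start on the visit date would give such subjects their old dose, so the repair has to keep that feature.

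**Conclusion.** The derivation is wrong as written for a visit at which an unchanged dose opens no record. On the most natural reading, that is Week 2. The Week 2 assigned dose is then missing for unchanged subjects, or is the dose of a later unscheduled change, contrary to the SAP's own definition. The most recent dose before Week 4 is missing for subjects with no record in between, apart from those covered by the permanent-stop fallback.

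The effect is confined to exploratory displays at those two points. The named timepoints for assigned dose (Day 1, Week 28, Week 52 and yearly), those for most recent dose (Week 28, Week 52, yearly and End of Treatment), the Hgb summaries and all tested endpoints are untouched. The size is unknown; the figures above rest wholly on assumed shares.

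Three stronger readings are tempting and are not supported:

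- A reader might infer that the gap recurs at every visit. Footnote 9 is attached to no other scheduled visit.
- A reader might infer that most recent dose is also reported wrongly. A dose changed at an unscheduled visit between Week 2 and Week 4 is the right answer there.
- A reader might infer that the clopidogrel dose-adjustment table, which "will be summarized at Week 2 and Week 4 by baseline clopidogrel co-administration", loses its category for no change. Section 8.2.9 does not say that this table is built from assigned dose, so this does not follow.

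**What to change.** In Section 10.6.3.6, for assigned dose at Visit X:

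- Keep the current rule for a record that arises from the dosing instruction at Visit X, including one that starts shortly after the visit.
- Do not use a record that arises from a later unscheduled visit.
- If there is no record from Visit X and the subject is still on randomized treatment, use the dose of the exposure record ongoing on the visit date, or the IRT-assigned dose.
- Leave the value missing when the visit was skipped.

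For most recent dose prior to Visit X, use the latest exposure record starting before Visit X, with no lower limit on its start date. Keep the existing provision for permanent stoppers, and carry nothing past it.

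It would also help to state whether a Week 2 hand-back of unchanged supply opens an exposure record.

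The exposure start and stop dates are already collected, as the exposure listing in Section 6.2.6 shows, so no new data are needed. The cost is a small programming change and a rule for linking each record to the visit that produced it. No dosing rule is involved.

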10.6.3.7. Phosphate Binder Use

Phosphate Binder Use
Baseline Phosphate Binder Use (Yes/No)

 Baseline Phosphate binder use will be categorized as either Yes, or No for the phosphate binder analyses. Subjects will be counted in each applicable group, based on the concomitant medications they are receiving on the day of randomization.
Phosphate Binder Use at Week 28 (Yes/No)

 Phosphate binder use at Week 28 will be categorized as either Yes, or No for the phosphate binder analyses. Subjects will be counted in each applicable group, based on the concomitant medications they are receiving between Week 24 and Week 28.
Phosphate Binder Use at Week 52 (Yes/No)

 Phosphate binder use at Week 52 will be categorized as either Yes, or No for the phosphate binder analyses. Subjects will be counted in each applicable group, based on the concomitant medications they are receiving between Week 48 and Week 52.

10.6.4. Safety

10.6.4.1. CV Safety Endpoints

CV Safety Endpoints
Dates for Investigator Reported CV Safety Endpoints

 All-cause hospitalization: admission date All-cause hospital re-admission: admission date within 30 days following a discharge date Death: date of death from the Death1 eCRF page Myocardial infarction: date of onset of Myocardial Infarction/Unstable Angina symptoms from the MI/UA1 eCRF page Stroke: start date of neurological symptoms from the Stroke/TIA eCRF page Hospitalization for HF: Earliest of (ER admission date, Hospital admission date) from Heart Failure eCRF page Thromboembolic event: date of onset of thromboembolic event from the Thromboembolic Event eCRF page
Dates for Adjudicated CV Safety Endpoints

 Death: event date reported by CEC

CV Safety Endpoints

- Myocardial infarction: event date reported by CEC
 - Fatal MI events only identified through a primary cause of death, without a corresponding positively adjudicated MI event: death event date reported by CEC
- Stroke: event date reported by CEC
 - Fatal stroke events only identified through a primary cause of death, without a corresponding positively adjudicated stroke event: death event date reported by CEC
- Hospitalization for HF: event date reported by CEC
 - Fatal heart failure/cardiogenic shock events only identified through a primary cause of death, without a corresponding heart failure event: death event date reported by CEC
- Thromboembolic event (DVT, PE, VAT): event date reported by CEC
 - Fatal PE events only identified through a primary cause of death, without a corresponding positively adjudicated PE event: death event date reported by CEC

Due to the design of the CRF, a fatal MI is reported as both an MI and a death. Both of these events will go through the adjudication process. It is possible that the MI could be negatively adjudicated, while the death is positively adjudicated with a primary cause of acute MI. The rationale for this is that the definition of a positively adjudicated MI (contained in the CEC charter) is more explicit than the definition of acute MI as a primary cause of death. Therefore, in analyses that include MI events without including all-cause mortality, the primary approach will be to include only those fatal MI events that correspond to a positively adjudicated MI event. These analyses will then be repeated for supportive purposes using all fatal MI events – including those fatal MI events only identified through a primary cause of death (i.e., acute MI) without a corresponding positively adjudicated MI event.

Additionally, a fatal MI event could have an event date that differs from the death date because the subject may have died as a result of the MI but not on the same day. For analysis of first occurrence MACE, MI or any other composite endpoint that includes both MI and death, if both the MI and death events are positively adjudicated, the MI date will be used as the event date. For analysis of CV mortality only and all-cause mortality only, the death date will be used.

Similarly, fatal stroke events are reported as both a stroke and a death. In analyses that include stroke events without including all-cause mortality, the primary approach will be to include only those fatal stroke events that correspond to a positively adjudicated stroke event. These analyses will be repeated for supportive purposes using all fatal stroke events – including those fatal stroke events only identified through a primary cause of death (i.e., stroke) without a corresponding positively adjudicated stroke event. For analysis of first occurrence MACE, stroke, or any other composite endpoint that includes stroke and death, if both the stroke and death events are positively adjudicated, the stroke date will be used as the event date. For analysis of CV mortality only and all-cause mortality, the death date will be used.

Fatal heart failure events are reported as both a heart failure and a death. In analyses that include hospitalization for heart failure events without including all-cause mortality, a single approach which includes only those fatal hospitalization for heart failure events that correspond to a positively

CV Safety Endpoints

adjudicated hospitalization for heart failure event will be used. The definition of the hospitalization for heart failure endpoint includes requirements around hospitalization which are not captured in the associated primary cause of death (heart failure/cardiogenic shock), so identification of hospitalization for heart failure events through only a primary cause of death is not possible. However, supportive analyses of the hospitalization for heart failure endpoint may include all heart failure events. These supportive analyses would then be able to include fatal heart failure events from the death page (i.e. primary cause of death = heart failure/cardiogenic shock) that do not correspond to a positively adjudicated heart failure event. For analysis of hospitalization for heart failure or any composite endpoint that includes hospitalization for heart failure and death, if both the hospitalization for heart failure and death events are positively adjudicated, the hospitalization for heart failure date will be used as the event date. For analysis of CV mortality only and all-cause mortality, the death date will be used.

Fatal pulmonary embolism events are reported as both a pulmonary embolism and a death. In analyses that include pulmonary embolism events (i.e., thromboembolic events) without including all-cause mortality, the primary approach will be to include only those fatal pulmonary embolism events that correspond to a positively adjudicated pulmonary embolism event. These analyses will be repeated for supportive purposes using all pulmonary embolism events – including those fatal pulmonary embolism events only identified through a primary cause of death (i.e., pulmonary embolism) without a corresponding positively adjudicated pulmonary embolism event. For analysis of pulmonary embolism or any composite endpoint that includes pulmonary embolism and death, if both the pulmonary embolism and death events are positively adjudicated, the pulmonary embolism date will be used as the event date. For analysis of CV mortality only and all-cause mortality, the death date will be used.

In the situation that there is a fatal MI (or fatal stroke, hospitalization for heart failure, or pulmonary embolism) that does not have both an MI (or stroke, hospitalization for heart failure, or pulmonary embolism) endpoint and a death endpoint reported, the date of the event that is reported will be used in the analysis of all relevant endpoints. This would additionally apply to situations where the MI (or stroke, hospitalization for heart failure, or pulmonary embolism) may occur within an analysis period and the death may occur outside of the analysis period; the endpoint with the date in the analysis period will be used for all relevant endpoints.

Missing or Partial Endpoint Dates

Missing or Partial Event (Start) Dates

- If event dates are missing or partial and there is not sufficient information to classify the time period of the event, the event will be classified as occurring on-treatment and post-randomization. The event will also be considered to have occurred during the follow-up for cardiovascular events as defined in Section 10.6.4.
- The following rules for missing or partial event dates for events other than death will be implemented as long as the imputed date is after the randomization date. If the imputed date is prior to the randomization date, then the date of randomization will be imputed for the event date.
 - If only the day of the month is missing, impute the first day of the month (e.g., --FEB2016 would impute as 01FEB2016)
 - If the month and day of the month are missing, impute 01JAN (e.g., ----2016 would

CV Safety Endpoints

- impute as 01JAN2016)
 - If the year, month, and day of month are missing, impute the randomization date
- The following rules for missing or partial death dates will be implemented as long as the imputed date is after the randomization date. If the imputed date is prior to the randomization date, then the date of randomization will be imputed for the death date.
 - The latest clinic visit, telephone visit, other contact with subject visit, CV endpoint (other than death), AE or SAE date, or date last known to be alive will be determined. If the year, month, and day of month of the death are missing then the death date will be imputed as the latest of the dates.
 - If only the day of the month of death is missing, then impute the first day of the month (e.g., --FEB2016 would impute as 01FEB2016). However, if this imputed date results in a date that is prior to the latest clinic visit, telephone visit, other contact with subject visit, CV endpoint (other than death), AE or SAE date, or date last known to be alive then impute the missing day of death as equal to this date instead. For example:
 - If --FEB2016 is given as the death date and there is a non-fatal MI on 08FEB2016, then the imputed date of death would be 08FEB2016 rather than 01FEB2016 such that the death is not before the non-fatal MI.
 - If --MAR2016 is give as the death date and the latest date is a non-fatal MI on 08FEB2016 then the imputed date of death would be 01MAR2016.
 - If the month and day of the month of death are missing, then impute as 01JAN (e.g., ----2016 would impute as 01JAN2016). However, if this imputed date results in a date that is prior to the latest clinic visit, telephone visit, other contact with subject visit, CV endpoint (other than death), AE or SAE date, or date last known to be alive then impute the missing month and day of death as equal to this date instead. For example:
 - If ----2016 is given as the death date and the latest date is a non-fatal MI on 08FEB2016 then the imputed date of death would be 08FEB2016 rather than 01JAN2016 such that the death is not before the non-fatal MI.
 - If ----2017 is given as the death date and the latest date is a non-fatal MI on 08FEB2016 then the imputed date of death would be 01JAN2017.
 - For deaths that occur after subjects have prematurely withdrawn from the study, missing or partial dates will be imputed as specified above except if the imputation places the death prior to or on the premature withdrawal date. In this case the death date will be imputed as the premature withdrawal date.
- If both death and study completion/withdrawal have missing or partial dates, they will be imputed as specified (see Section 10.6.1 and Section 10.6.4). If the imputed death date is prior to the imputed study completion/withdrawal date, then the study completion/withdrawal date will use the imputed death date instead.

Missing or Partial Hospitalization End Dates

- If hospitalization end dates are missing or partial, the following rules for missing or partial dates will be implemented as long as the imputed date is before the next hospitalization start date or study completion/withdrawal date (if there is no next hospitalization start date). If the imputed date is after the next hospitalization start date, then the date of the next hospitalization start

CV Safety Endpoints

date – 1day will be used as the hospitalization end date. If the imputed date is after the study completion/withdrawal date, then the date of the study completion/withdrawal date will be used as the hospitalization end date.
 
 ○ If only the day of the month is missing, impute the last day of the month (e.g., --MAR2016 would impute as 31MAR2016) ○ If the month and day of the month are missing, impute 31DEC (e.g., -----2016 would impute as 31DEC2016) ○ If the year, month, and day of month are missing, impute the date of study completion/withdrawal.
Order of CV Safety Endpoint Events

 • If multiple events occur on the same day or have imputed dates that place them on the same day, but it is not clear which event occurred first, then the following order will be applied: 
 1. MI 2. Stroke 3. Hospitalization for Heart Failure 4. Thromboembolic Event: DVT 5. Thromboembolic Event: VAT 6. Thromboembolic Event: PE 7. Death
CV Mortality

 • CV mortality includes all deaths indicated as having a cardiovascular primary cause of death (including fatal MI and fatal stroke events) as well as deaths with an undetermined primary cause of death that are indicated to be either presumed sudden death or presumed cardiovascular death. Deaths with an undetermined primary cause of death that are indicated to be an unknown death will not be included as a CV mortality event.
Heart Failure Events

 • The primary heart failure event of interest in this study is hospitalization for heart failure. However, investigators are requested to report all potential heart failure events for adjudication, even if there was no hospitalization associated with the event. • The CEC will categorize heart failure events into one of the following adjudicated event types: 
 ○ Hospitalization for Heart Failure ○ Urgent ER/ED Visit for Heart Failure ○ Urgent Office/Practice Visit for Heart Failure ○ Negative adjudication (i.e., not one of the heart failure events above) • For purposes of endpoints that contain hospitalization for heart failure as a component, only the events adjudicated by the CEC as Hospitalization for Heart Failure will be included. • The concordance table for heart failure events will include the 4 adjudicated event types listed above.
Investigator-reported Endpoint Events for Concordance

 • For purposes of concordance tables, events with an investigator-reported event date \geq randomization date during the time period for follow-up of cardiovascular events, that meet the following final diagnosis criteria will be considered to be investigator-reported endpoint events:

CV Safety Endpoints

Endpoint	Investigator-reported final diagnosis (from eCRF)
Myocardial infarction	Myocardial infarction
Stroke	Primary ischemic stroke (with or without hemorrhagic transformation), Primary intracranial hemorrhage, Retinal/ocular hemorrhage or infarction, Unknown type of stroke
Hospitalization for Heart Failure	Systolic heart failure, Diastolic heart failure, Heart failure - unspecified type Additional criteria: If admission/discharge times are non-missing, at least one of the following must be true (1-3): 1. Time in hospital is ≥ 24 hours 2. Time in ED/ER is ≥ 24 hours 3. Consecutive time in hospital + time in ED/ER is ≥ 24 hours Or if admission/discharge times are missing, then at least one of the following must be true (4-6): 4. Change in calendar date between hospital admission and discharge 5. Change in calendar date between ED/ER admission and discharge 6. Change in calendar date between consecutive hospital and ED/ER admission and discharge
Thromboembolic Event (DVT, PE, VAT)	Deep Vein Thrombosis (DVT), Pulmonary Embolism (PE), Vascular Access Thrombosis
All-cause mortality	Any death record
CV mortality	Any Cardiovascular primary cause of death
Non-CV mortality	Any Non-Cardiovascular primary cause of death
Unknown (sub-category of All-cause mortality)	Any Unknown primary cause of death

Events with an adjudication record, but without an investigator reported record, will also be included in the concordance summaries.

All-cause Hospitalization and All-cause Hospital Re-admission within 30 days

- All-cause hospitalization events are defined to be hospital admissions recorded on the Hospitalization eCRF form with a hospitalization duration ≥ 24 hours.
- All-cause hospital re-admissions within 30 days are defined to be hospital admissions recorded on the Hospitalization eCRF form with a hospitalization duration of ≥ 24 hours and an admission date within 30 days following a previous discharge date of an all-cause hospitalization event, where the previous hospitalization should be \geq as stated above.
- Hospitalization rate (per year) across the study = number of all-cause hospitalization events / [follow-up time (days) / 365.25].
- All-cause hospital re-admission rate (per year) across the study = number of all-cause hospital re-admissions / [follow-up time (days) / 365.25].

CV Safety Endpoints
General Definitions

 • Time to event (days) = date of event – randomization date +1 • Censored time (days) = censoring date – randomization date + 1 • First event person years = (cumulative total time to first event for subjects who have the event + cumulative total of censoring time for subjects without the event) / 365.25 • First event incidence rate (per 100 person years) = (100 * number of subjects with at least 1 event) / first event person years • First event absolute rate difference (per 100 person years) = daprodustat incidence rate (per 100 person years) – darbepoetin alfa incidence rate (per 100 person years)
Evaluation Time Periods for CV Endpoints
Time Period for Follow-up of Cardiovascular Endpoints
